During each Evaluable Period, a binary outcome variable will be defined to be 1 if the weekly stdKt/Vurea for a given week meets the success criteria and 0 otherwise. For each subject, this will result in approximately 5 binary outcome values for each period. Each subject will be considered as meeting the primary performance endpoint for that period if all weekly stdKt/Vurea values meet the performance success criterion. A Non-inferiority test will be conducted. The difference in proportion of subjects (P1-P2) meeting the performance criteria in the Unassisted Evaluation Period (P2) and the Assisted Evaluation Period (P1) will be reported with a two-sided 90% CI. If the Upper bound of the Confident interval is less than δ =0.10 then the null Hypothesis is rejected and non-inferiority is demonstrated.

Secondary Endpoints:

A descriptive summary of AEs including SAEs and other secondary endpoints will be provided. The details are provided later in the protocol.

Table 1: Schedule of Evaluations and Procedures

Observation	Screening	In-Facility Introduction Period	Transition Period A	Assisted Evaluable Period ^{10,11}	Assisted Evaluable Period Visit 1	Transition Period B	Unassisted Home Evaluable Period	Unassisted Evaluable Period Visit 2	End of Study or Early Termination Visit
Informed Consent of subject and care partner	X	# 2						3	
Demographics and medical history	X								
Selected laboratory and medication histories (within 30 days of screening)	X	9							
Physical examination	X				X			X	X
Vital signs ¹	X				X			X	X
12-lead ECG	X								X
Feed water analysis for the home	X	\$ **				3			
Home suitability assessment	X								
Clinical assessment by Investigator or designee ²	X	X	X	X	X	X	X	X	
Clinical observations ³	S 00	X	X	X		X	X		X
AE / SAE / ADE ⁴	X	X	X	X	X	X	X	X	X
Concomitant medications	X	X	X	X	X	X	X	X	X
Ultrafiltration ⁵		X	X	X		X	X		
Clinical laboratory examinations ⁶	X	X	X	X		X	X		X
Patient reported outcomes ⁷		X		X			X		X
HemoCare™ Hemodialysis System training		X	X	X					
Comprehension and retention testing ⁸		X		X			_		

- 1. Blood pressure, heart rate, respiratory rate, temperature (°F), height and weight are to be collected in a standardized manner in a sitting position after the patient has rested comfortably for 5 minutes.
- 2. A clinical assessment by the Investigator or designee will occur weekly throughout the study. A direct interaction with the subject is not required for this assessment.

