4.1 Objectives

4.1.1 Primary Objectives

Safety

To compare the safety of HemoCare™ Hemodialysis System, as measured by adverse events, between the Assisted and Unassisted Home Evaluable Periods.

Performance

To compare the performance of HemoCareTM Hemodialysis System, as measured by dialysis adequacy (weekly stdKt/V_{urea}), between the Assisted and Unassisted Home Evaluable Periods

4.1.2 Secondary Objectives:

- To compare descriptively all reported adverse events (AE) and serious adverse events (SAE; anticipated, unanticipated, and device-related) between the Assisted and Unassisted Home Evaluable Periods.
- 2. To assess the safety of the treatment, as measured by control of serum phosphorus levels, during the Assisted and Unassisted Home Evaluable Periods.

- 3. To assess the safety of the treatment, as measured by control of serum potassium levels, during the Assisted and Unassisted Home Evaluable Periods.
- 4. To evaluate UF data within and between the Assisted and Unassisted Home Evaluable Periods, as assessed by the difference between the fluid weight removed as measured by the device and the subject's weight change as measured by a scale.

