9.1 General Considerations

Further details of the planned statistical methods presented below will be provided in the study statistical analysis plan (SAP). The purpose of the SAP is to further elaborate the statistical methods described in the protocol and describe analysis conventions to guide the statistical programming work. Any changes to the final SAP will be documented. Unless otherwise specified, treatment effects will be evaluated based on a 2-sided significance level of 0.050 (when rounded to 3 decimal places)

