9.5 Secondary Endpoints

 Adverse events will be mapped to a primary MedDRA System Organ Class (SOC) and Preferred Term (PT). Anticipated AEs and SAEs and unanticipated AEs and SAEs will be summarized during each Evaluable Period by SOC and PT. In addition, all devicerelated AEs and SAEs will be summarized during each Evaluable Period by SOC and PT.

An overview of the total number of AEs and SAEs (anticipated, unanticipated, and device-related) during each Evaluable Period will be provided. In addition, for each Evaluable Period an overview will be provided of the total number of subjects having at least 1:

- Anticipated AE
- Anticipated SAE
- Unanticipated AE
- Unanticipated SAE
- Device-related AE
- Device-related SAE

The proportion of subjects having at least one AE within each of these six AE subgroups will be compared between Evaluable Periods with exact McNemar's tests. For each of these six AE subgroups the hypotheses will be:

$$H_0: P_u = P_a$$

 $H_a: P_u \neq P_a$

Where P_u = Proportion of subject having at least 1 event during unassisted treatments and P_a is the proportion of subjects having at least 1 event during the Assisted treatments.

Identifying the number of subjects who had at least 1 event during assisted treatment and no event during unassisted treatment as n_{12} , and subjects who have no event during assisted treatment and at least 1 event during unassisted treatment as n_{21} , the indicator

$$Q = \frac{(n_{12} - n_{21})^2}{(n_{12} + n_{21})}$$
 will be compared to x^2 with 1 Degree of Freedom if

$$(n_{12} + n_{21}) > 20$$
. Otherwise the correction $Q = \frac{(|n_{12} - n_{21}| - 1)^2}{(n_{12} + n_{21})}$ will

be used. The Null Hypothesis will be rejected if the P-value for the x^2 is less than 0.10.

No multiplicity adjustment will be done for these secondary endpoints.

Furthermore, the proportion of subjects having AEs within each of these six AE subgroups will be summarized by SOC, PT and severity (mild, moderate or severe) during each Evaluable Period for the most severe rating of each AE per subject.

 The incidence of decreased serum phosphorus defined as at least 1 post-dialysis serum phosphorus level < 2.2 mg/dL, the incidence of elevated serum phosphorous defined as a least 1 post-dialysis serum phosphorus level > 5.5 mg/dL, will each be compared between Evaluable Periods with exact McNemar's tests.

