- 3. The incidence of decreased serum potassium defined as at least 1 post-dialysis serum potassium level of < 3.5 meq/L, and the incidence of elevated serum potassium defined as at least 1 post-dialysis serum potassium level of > 5.9 meq/L, will each be compared between Evaluable Periods with exact McNemar's tests.
- A descriptive summary of UF and target weight during each evaluable period will be provided.

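### Section 9.5 attaches a reject-at-0.10 rule to six adverse-event comparisons that secondary objective 1 and the synopsis call descriptive

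*Combined protocol and SAP*

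**What the plan says.** Secondary objective 1 (Section 4.1.2, repeated in the synopsis) is "To compare descriptively all reported adverse events (AE) and serious adverse events" between the two Evaluable Periods. On secondary endpoints, the statistical part of the synopsis says "A descriptive summary of AEs including SAEs and other secondary endpoints will be provided" and refers to later sections for detail.

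Section 9.5, item 1, defines six subgroups: anticipated, unanticipated and device-related events, each for AEs and for serious AEs (SAEs). The proportion of subjects with at least one event in "each of these six AE subgroups will be compared between Evaluable Periods with exact McNemar's tests". Each has a null of equal proportions, a two-sided alternative and a McNemar statistic Q. The decision rule follows: "The Null Hypothesis will be rejected if the P-value for the" chi-square statistic is below 0.10. Next comes "No multiplicity adjustment will be done for these secondary endpoints".

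Items 2 and 3 of Section 9.5 add low and high phosphorus and low and high potassium, which "will each be compared between Evaluable Periods with exact McNemar's tests". They give no level and no rejection rule. Section 9.1 sets the default: "Unless otherwise specified, treatment effects will be evaluated based on a 2-sided significance level of 0.050".

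**The concern.** A descriptive comparison and a hypothesis test with a rejection rule license different statements in the study report. Under objective 1 the sponsor would show counts and let clinical judgement work on them. Under Section 9.5 the sponsor can state that the two periods differ, or that the null was not rejected, for each of six AE categories. Nothing in the text available labels these results nominal or exploratory, and the synopsis's list of exploratory endpoints does not include them.

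The results are likely to be read closely. Section 9.2 rests the safety judgement on the rate and type of AEs and names device-related events, which make up two of the six subgroups. A chance rejection could be reported as a difference in either direction. With about 30 subjects and rare events, a non-rejection could be reported as evidence of no difference.

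**Working it through.** **The two descriptions side by side.** Objective 1: descriptive. Synopsis: descriptive summary, details later. Section 9.5: null and two-sided alternative, threshold 0.10, reject or not. The synopsis's deferral of details does not bridge the gap, because a rejection rule changes the status of the inference. For phosphorus and potassium the conflict is narrower: objectives 2 and 3 do not use the word descriptive, so only the synopsis sentence is at odds with testing them.

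**Inputs for the error rates.** Six tests, threshold 0.10 (chi-square critical value 2.706 on 1 df) and the Q formula come from Section 9.5. The n = 30 comes from Section 9.2, taken as 30 subjects with data in both periods. The discordance rate ψ, the share of subjects with an event in one period only, is not given, so a range is assumed. The 0.10 is a chosen level and the plan states no family-wise figure, so there is no plan figure to reproduce.

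**Rule.** With m = n12 + n21, Q = (|n12 − n21| − 1)²/m if m ≤ 20, and (n12 − n21)²/m if m > 20. Reject if Q > 2.706.

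**Size of one test under no difference.** Given m, n12 is Binomial(m, 0.5), so size = Σ over m of Bin(m; 30, ψ) × P(Q > 2.706 | m). For six independent tests, P(at least one rejection) = 1 − (1 − size)⁶.

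| ψ | size per test | at least one of six |
|---|---|---|
| 0.05 | 0.0009 | 0.5% |
| 0.10 | 0.0086 | 5% |
| 0.20 | 0.0315 | 17% |
| 0.40 | 0.0535 | 28% |
| 0.50 | 0.0612 | 31% |

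Example at ψ = 0.40: 1 − (1 − 0.0535)⁶ = 1 − 0.719 = 0.281.

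**Rare categories.** SAE subgroups will probably have few discordant subjects and add almost nothing. If only three categories are active, at ψ = 0.40: 1 − (1 − 0.0535)³ = 1 − 0.848 = 0.152, about 15%. A graded mix of 0.40, 0.30, 0.20, 0.15, 0.05 and 0.05 gives sizes of 0.054, 0.043, 0.032, 0.021, 0.001 and 0.001, and about 14% for the six.

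**False reassurance.** For a 4:0 split against unassisted treatment, Q = (4 − 1)²/4 = 2.25 < 2.706, so there is no rejection; exact p = 2 × (1/2)⁴ = 0.125. At 5:0, Q = (5 − 1)²/5 = 3.2 and exact p = 2 × (1/2)⁵ = 0.0625, so it rejects. At least five discordant subjects, all in one direction, are therefore needed before the rule can reject.

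**Exact test or chi-square.** Section 9.5 names an exact test but writes a chi-square Q. At 0.10 the two agree for every table with up to 20 discordant subjects, so the choice hardly affects the table above.

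**Laboratory comparisons.** Read literally, Section 9.1 puts them at 0.050. On that reading a 5:0 split (exact p = 0.0625) would reject for an AE category but not for potassium. The level could also be meant as 0.10 by analogy; the text does not say.

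**The case against.** The strongest reply is that this is safety monitoring and not a claim of benefit. Family-wise control makes harm harder to detect, and the plan openly states in advance that it will not adjust. No success criterion or stopping rule uses these tests. The primary safety analysis is the AE rate ratio with its 90% confidence interval, and Section 9.2 leaves the judgement of safety to clinical determination. All of that stands, and it is why adjustment is not requested here.

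It is also true that 0.10 does not contradict Section 9.1, which yields wherever another level is specified, and that it matches the 90% intervals of the primary endpoints. Sections 9.1 and 9.8 defer further detail to the SAP, so the missing nominal label can be asserted only for the text available.

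Three stronger readings are tempting, and the documents do not support them:

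- A reader might quote 1 − 0.9⁶ = 47% as the false-positive risk. That assumes each test attains its full 0.10. With 30 subjects the planned discrete test stays between 0.001 and 0.061 over the rates examined. The categories also overlap, since a subject with an anticipated SAE also has an anticipated AE.
- A reader might treat all ten comparisons as one family under the 0.10 rule. The rule is written only for the six AE subgroups, and the sentence on multiplicity sits under item 1.
- A reader might infer that a rejection would be declared a safety finding. The documents do not say what follows a rejection.

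None of this removes the mismatch between objective 1 and the decision rule.

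**Conclusion.** The inconsistency is real and lies in the wording: Section 9.5 turns a comparison called descriptive into six formal tests without saying that their results are nominal. The chance of at least one false rejection is moderate at most, about 5% to 28% for discordance rates of 10% to 40%, and about 15% if only three categories are active. These figures assume 30 paired subjects, no true difference, a common discordance rate across the active categories, and independence between categories; the documents give no discordance rate. The opposite misreading matters at least as much, because even a 4:0 split against unassisted treatment does not reject. The absence of a multiplicity adjustment is not itself a fault. The laboratory comparisons are a lesser matter: an unstated level, and a conflict with one synopsis sentence only. The plan should be changed, but no primary conclusion depends on it.

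**What to change.** In Section 9.5, delete the sentence that rejects the null at p < 0.10. State that the six AE comparisons are descriptive, as objective 1 says. For each one, report the discordant counts (n12, n21), the paired difference in proportions with a confidence interval, and a nominal unadjusted p-value. Say explicitly that neither a difference nor the absence of one will be concluded from these p-values. Present the four phosphorus and potassium comparisons in the same way, which also removes the question of their level. Carry the same wording into the SAP.

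The cost is wording only: no extra subjects, data or visits. The downside is that the sponsor gives up formal significance statements on these secondary endpoints.

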- 3. The comprehensive metabolic panel includes glucose, calcium, sodium, potassium, total CO₂ (or serum bicarbonate), chloride, urea, creatinine, ALP, ALT, AST, total bilirubin, serum albumin and total protein. In addition to serum phosphorus, the metabolic panel will be performed at screening and monthly during the study.
- 4. Pre- and post-dialysis serum potassium and serum phosphorus will be collected twice per week during Transition Period A and monthly for the remainder of the study
- 5. Kt/V is derived from pre-dialysis and post-dialysis serum urea levels. It will be performed once during Screening and the In-Facility Introduction Period, then every two weeks starting in the Assisted Evaluable Period.
- 6. aPTT will be measured at the first treatment with HemoCareTM during the In-Facility Introduction Period, Transition Period A, and the Assisted Evaluable Period to assess anticoagulation
 At the discretion of the Investigator, additional aPTT testing may be performed to assist with heparin dosing.

Figure 1: Flow of activities:

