4.2.2 Secondary Endpoints

- 1. Number of anticipated and unanticipated AEs and SAEs during each Evaluable Period including number of device-related AEs and SAEs.
- Incidences of decreased and increased post-dialysis serum phosphorus during each Evaluable Period.
- Incidences of decreased and increased post-dialysis serum potassium during each Evaluable Period.
- 4. A descriptive summary of UF and target weight during each Evaluable Period.

5 Study Population

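### The elevated phosphorus and potassium endpoints count only post-dialysis values, so a null result says little about control; add a paired analysis of the pre-dialysis values already drawn

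*Combined protocol and SAP*

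**What the plan says.** Section 4.1.2 sets the second secondary objective: "To assess the safety of the treatment, as measured by control of serum phosphorus levels, during the Assisted and Unassisted Home Evaluable Periods". The third is the same for potassium.

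Section 4.2.2 turns these into endpoints on one sampling time for both directions: "Incidences of decreased and increased post-dialysis serum phosphorus during each Evaluable Period" and "Incidences of decreased and increased post-dialysis serum potassium during each Evaluable Period". Section 9.5, items 2 and 3, gives the limits. A subject counts as elevated in a period with at "least 1 post-dialysis serum phosphorus level > 5.5 mg/dL", or with "at least 1 post-dialysis serum potassium level of > 5.9 meq/L". Low values are likewise post-dialysis (below 2.2 mg/dL and below 3.5 meq/L). Each incidence is compared between periods by exact McNemar test.

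The pre-dialysis counterpart is collected. Table 2, footnote 4: "Pre- and post-dialysis serum potassium and serum phosphorus will be collected twice per week during Transition Period A and monthly" for the rest of the study. The pre-dialysis metabolic panel plus phosphorus is also monthly. No endpoint in 4.2.2 and no analysis in the visible text of section 9 uses a pre-dialysis phosphorus or potassium value. The exploratory endpoints in the protocol summary (reliability, training, questionnaires, alarms) do not mention either analyte.

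**The concern.** A post-dialysis sample suits the low side, where the worry is over-removal. It is a weak basis for the high side. The level builds up between treatments, and the endpoint reads it just after a long treatment whose phosphate removal the protocol's own rationale (section 2.1) rates above that of conventional dialysis.

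The comparison of interest is professional versus unassisted administration. The plan foresees longer gaps between treatments (section 3.3) and device holidays (section 9.7.1). Accumulation over such gaps shows first in the pre-dialysis value, and the sampled treatment then lowers it before the only measurement the endpoint counts. At stake is a table with few or no elevated subjects in either period, read as evidence of control when the sampling time may explain it.

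**Working it through.** The plan states no expected incidence, power or reduction ratio for these endpoints, so there is no figure to reproduce.

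**1. Direction, without assuming an incidence.** If a treatment lowers the analyte, post-dialysis is below pre-dialysis. Every post-dialysis value above a limit then had a pre-dialysis value above the same limit, but not the reverse. At any given limit, the post-dialysis definition can only miss elevations.

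**2. How high the pre-dialysis value must be.** Value needed = limit / (1 - fractional fall). The falls are assumptions. The 10% row is a deliberately mild case.

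| Assumed fall | Phosphorus, limit 5.5 mg/dL | Potassium, limit 5.9 meq/L |
|---|---|---|
| 10% | 5.5/0.9 = 6.1 | 5.9/0.9 = 6.6 |
| 20% | - | 5.9/0.8 = 7.4 |
| 30% | 5.5/0.7 = 7.9 | 5.9/0.7 = 8.4 |
| 40% | 5.5/0.6 = 9.2 | 5.9/0.6 = 9.8 |
| 50% | 5.5/0.5 = 11.0 | - |
| 60% | 5.5/0.4 = 13.8 | - |

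With the smallest fall in each main range (30% and 20%), a subject with phosphorus 7 or potassium 6.5 before every sampled treatment ends at 7 x 0.7 = 4.9 or 6.5 x 0.8 = 5.2. Neither is counted as elevated.

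**3. Samples per period.** Section 9.2 gives 34 treatments at 3.5 per week: 34/3.5 = 9.7 weeks, or 68 days at one treatment every other day. Monthly sampling gives about 2 to 3 samples. If one sample has an assumed 0.5% to 2% chance of being elevated, subject-level incidence is between 1 - 0.995^2 = 1% and 1 - 0.98^3 = 6%.

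**4. What the test needs.** With all k discordant subjects in one direction, exact two-sided McNemar p = 2 x 0.5^k: 0.125 for k = 4, 0.0625 for k = 5, 0.031 for k = 6. The minimum is 6 for p < 0.05 (the default level in section 9.1) and 5 for p < 0.10 (the level written under item 1 of section 9.5). Items 2 and 3 state no level of their own. The continuity-corrected statistic in section 9.5 gives the same minimum counts (5-0: p = 0.074; 6-0: p = 0.041).

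**5. Power.** Exact enumeration with 30 subjects, responses in the two periods independent within subject, and assumed incidences:

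| Assisted vs unassisted | Power at 0.05 | Power at 0.10 |
|---|---|---|
| 2% vs 5% | 0.2% | 0.9% |
| 2% vs 10% | 4.4% | 10.8% |
| 2% vs 20% | 41.5% | 57.0% |
| 20% vs 40% | 28% | 41% |
| 20% vs 50% | 59% | 71% |

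The first two rows show an endpoint that stays rare in both periods: the test has almost no chance of detecting a change. The third shows that a gross loss of control could still register. The last two show that an incidence based on pre-dialysis values would be only moderately powered, so a continuous paired summary should accompany it.

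**The case against.** The strongest reply is that the trial does not rely on this endpoint to notice loss of control. Section 8.3.1 notifies the investigator of any laboratory value outside the normal range, before or after dialysis. Sections 8 and 8.3.1 make a laboratory abnormality an adverse event if it leads to intervention, and Appendix 1 defines hyperkalemia and hyperphosphatemia without stating sample timing. Such events would enter the primary safety rate and the tables of anticipated events. Missed and shortened treatments are classified directly (section 7.3), and delivered dose is a primary endpoint measured every two weeks. The post-dialysis limits also match the laboratory alerts in section 7.8, and pre-dialysis values additionally reflect diet and phosphate binders.

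Much of this stands. A reader might infer that the pre-dialysis values go unused; they do not, since they feed investigator review and possible adverse event reporting. Nor can it be said that the full plan never analyses them: section 9.6 is not visible, and section 9.8 refers further analyses to an SAP whose separate text is not in the combined document.

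Two things remain. Adverse event capture depends on intervention, discontinuation or a protocol limit, so it is not a between-period comparison of laboratory control. And treatment completion and urea-based dose are different quantities from phosphorus and potassium, to which the protocol gives objectives of their own.

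**Conclusion.** The point holds for the elevated side only. The definitions use the sampling time least able to show loss of control, and the visible section 9 leaves the paired pre-dialysis values out of every endpoint and analysis. A null McNemar result on elevated values would be weak evidence of control.

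That the definition can only miss elevations at a given limit requires only that treatment lowers the analyte. That elevated results are likely to be rare rests on the assumed falls. A reader might go further and infer that incidence will be near zero, or that the endpoint cannot show loss of control. The documents support neither: they give a direction for phosphate removal, no reduction ratio for either analyte and no expected incidence. An elevated post-dialysis value would still signal gross failure, and the post-dialysis definitions of low values are sensible. The primary endpoints are not affected. This is a low-cost improvement to two secondary objectives.

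**What to change.** In section 9.5, items 2 and 3, and in the SAP, with a matching entry in section 4.2.2:

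- Add a pre-specified paired between-period analysis of pre-dialysis phosphorus and potassium: the within-subject change in period mean with a confidence interval, plus the incidence above a limit the sponsor states in advance. Give the confidence level.
- Name this analysis as the main evidence on the elevated side.
- Keep the post-dialysis definitions for low values, and report the post-dialysis elevated count descriptively.
- State the source of the pre-dialysis limit. For potassium, section 9.5 uses 5.9 meq/L and Appendix 1 uses 5.6 mEq/L for hyperkalemia; the passages need reconciling.

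The cost is wording and a little more analysis, with no new sample or visit. The reported incidence of elevated values will probably be higher, and the text should say that this follows from the sampling time. The change concerns analysis variables only; alert limits and patient management are not addressed.
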